Children in the control group receive methotrexate and folic/folinic acid as per the physician's usual practice. Those who report nausea/vomiting during regular care are prescribed ondansetron at the same dose and schedule as above, as per the attending rheumatologist's discretion. This is the current practice at BC Children's Hospital and other Canadian centres.

Ondansetron is offered in three forms: tablets (4mg, 8mg), oral solution (4mg/5ml) and oral disintegrating tablets (4mg, 8mg). Tablets can be swallowed or crushed and mixed with food. Ondansetron will be prescribed as tablets, unless the physician and family decide to use liquid or oral disintegrating tablets instead. The dose will be the same.

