6.2 Inclusion-Exclusion Criteria and General Study Population

(ICH E3;9.3. ICH E9;2.2.1)

Subject inclusion criteria:

1. Ages 4-16 years
2. Diagnosis of JIA as per International League of Associations for Rheumatology ILAR criteria [14]
3. Followed at a CAPRI centre in Canada
4. Starting methotrexate to control JIA manifestations (arthritis, uveitis, psoriasis). (Female subjects of child bearing potential who are taking methotrexate for JIA cannot be pregnant, breastfeeding, or planning a pregnancy while on the drug and females of childbearing potential who are sexually active must use highly effective medically acceptable contraception. Subjects who stop methotrexate during the study will also discontinue ondansetron.)
5. Informed written consent to participate
6. Participating in the CAPRI JIA Registry

Subject exclusion criteria:

1. Previous use of methotrexate
2. Known hypersensitivity to ondansetron or any components of its formulations
3. Known hypersensitivity to other 5-HT3 antagonists
4. Known congenital Long-QT syndrome
5. Patients taking other medicinal products that lead to either QT prolongation or electrolyte abnormalities
6. Because the serotonin syndrome may occur when ondansetron is combined with other agents that may affect the serotonergic neurotransmitter system, patients receiving any of the serotonergic and/or neuroleptic drugs listed below will be excluded:
 - Triptans, SSRIs, SNRIs, lithium, sibutramine, fentanyl and its analogues, dextromethorphan, tramadol, tapendadol, meperidine, methadone, pentazocine or St. John's Wort (*Hypericum perforatum*), MAOIs, linezolid, methylene blue.
7. Patients who are pregnant or breastfeeding, or are sexually active and unwilling to practice an acceptable method of birth control.
8. Family unable to complete questionnaires in English or French

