6.3 Randomization and Blinding

(ICH E3; 9.4.3, 9.4.6. ICH E9; 2.3.1, 2.3.2)

Patients are assigned 1:1 online after confirming eligibility, using the Registry and block randomization by Canadian region and patient weight to one of two groups:

Intervention	routine premedication with oral ondansetron (2 mg if <15Kg, 4 mg if 15-30Kg, 8 mg if >30Kg; 3 doses a week)
Control	oral ondansetron at the same dosing, prescribed only to those who develop methotrexate-induced nausea/vomiting during usual care.

There is no blinding (masking) of treatment assignment.

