8.2 Analysis Populations

(ICH E3; 9.7.1, 11.4.2.5. ICH E9; 5.2)

The primary analysis will be conducted on the intention-to-treat population, including all randomized subjects. A secondary per-protocol analysis will be conducted on those subjects who received the assigned intervention for at least 3 months (ondansetron and methotrexate in the intervention group, methotrexate in the control group). Because it was clear at the time of interim analysis that some patients stopped methotrexate before 3 months due to intolerance, the per protocol analysis was modified to also include patients who stopped the medication before 3 months due to intolerance or toxicity.

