9.3 Protocol Deviations

1. Patient exclusions: The primary analysis is an intention to treat analysis. As such, a randomized patient can only be excluded from the primary analysis in exceptional circumstances, such as the diagnosis of JIA proves to be wrong, or the patient was included in violation of the inclusion and exclusion criteria for the trial. For further clarity, a patient randomized to intervention cannot be excluded because they did not take ondansetron or because they withdrew from the trial. A patient randomized to control cannot be excluded because they took ondansetron or because they withdrew from the trial. To preserve the

integrity of an intention to treat analysis it thus follows that all randomized patients should have a value for the primary endpoint. Due to OPT-JIA study design with no fixed date visits and missing data, it was clear at the time of the interim analysis that there would be patients with no documented endpoint at 12 months. Instead of imputing the endpoint as failure for subjects with no documented endpoint at 12 months or having their last recorded information carried forward, it was decided to use Kaplan Meier estimates of the probability of success at 12 months as these account best for censored patients and missing information.

The secondary per protocol analysis will include all patients that received the assigned intervention for at least 3 months or who experienced intolerance within the first three months. For the intervention group this means the patient received methotrexate and prophylactic ondansetron for at least 3 months. For the control group this means the patient received methotrexate for at least 3 months. Patients that withdraw or are lost to follow-up before 3 months are not included in the per-protocol analysis, unless they already experienced intolerance or toxicity. Patients who withdraw or are lost to follow-up after 3 months will be considered censored and have their data analyzed using Kaplan Meier survival methods.

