10.1 Primary Efficacy Analysis

The primary efficacy analysis is an intention to treat analysis comparing all subjects randomized to intervention to all subjects randomized to control. The primary efficacy analysis will include one primary endpoint and five secondary endpoints as described below.

Proportion of children who remain on methotrexate with no intolerance one year after starting methotrexate (Primary Endpoint): The primary endpoint (remain on methotrexate with no intolerance one year after starting methotrexate) has two components ("remain on methotrexate" and "no intolerance"). At every visit to the clinic the physician reports whether the patient is receiving methotrexate (MTX = 1) or not (MTX = 0). Temporarily not taking (holding) methotrexate due to intercurrent illnesses, running out of the medication, or similar reasons will not be considered a failure. If the reason for not taking methotrexate at one visit is unclear after review of the full record by the principal investigator, records will be verified with the site investigator. No intolerance means no MISS score of 6 or more points was ever recorded for that patient during the 52-week trial. Since the actual date the first methotrexate dose is given at home varies from family to family and it is not reliably recorded, we use the date of enrolment in OPT-JIA to calculate the 52 weeks of trial duration. Since OPT-JIA is a pragmatic trial and does not have study-specific visits, the visit

closest to 52 weeks is used, with a broad window of observation of 8 weeks before and 8 weeks after 52 weeks. To clearly differentiate between patients who dropped out and those who simply didn't have a visit on time, all available registry visits for all OPT-JIA participants will be provided to conduct the final analysis. Patients will be counted as successes rather than as censored if they have further registry visits beyond 52 weeks and had no failed before 52 weeks.

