10.2 Secondary Efficacy Analyses

There will be one secondary per-protocol efficacy analysis comparing all intervention and control subjects who received the assigned intervention for at least 3 months. The per-protocol analysis will be identical to the intention to treat analysis, except for the number of subjects included. For further clarity, it will consist of analyses of the same primary endpoint and five secondary endpoints, but only subjects that received the assigned intervention for 3 months will be included in comparisons. Because some patients may stop methotrexate due to intolerance before 3 months it was decided to conduct a modified per protocol analysis. The modified per-protocol analysis will include all patients receiving study medications for at least 3 months and all patients stopping medications before 3 months due to intolerance or toxicity. Physicians and parents are asked to report in separate case report forms if the patient is receiving ondansetron. If information is missing from one source, the other source will be considered true. If information is missing from both sources, the site investigator will be asked to verify ondansetron status against their clinical records.

11 Safety Analyses

OPT-JIA will assess the safety and tolerability of premedication with ondansetron, compared to as needed use. The safety endpoints are the frequency and cumulative incidence of adverse events and any serious unexpected suspected adverse drug reactions (SUSARs). Safety parameters in the OPT-JIA trial will be assessed using the standard set of questions about adverse events that are part of the CAPRI JIA Registry. These questions will be asked from the attending physician every time the study participant attends the pediatric rheumatology clinic for a medical visit. The form lists the following adverse events: abdominal pain, nausea/vomiting, rash (not JIA rash), injection reaction, infusion reaction, gastrointestinal bleed, abnormal blood counts, abnormal liver function tests, anaphylaxis, infection with hospitalization, tuberculosis, opportunistic infection, demyelinating disease, inflammatory bowel disease, malignancy, gastrointestinal perforation, eye surgery, joint surgery, and macrophage activation. Any non-listed events are reported as "Other / Not listed" by entering a description of the adverse event.

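### The per-protocol rule sets no ondansetron condition for controls, so a control on routine ondansetron from the start counts as adherent

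*SAP*

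**What the plan says.** Section 6.3 gives controls ondansetron "prescribed only to those who develop methotrexate-induced nausea/vomiting during usual care". Section 6.1 agrees: "Those who report nausea/vomiting during regular care are prescribed ondansetron at the same dose and schedule as above", at the rheumatologist's discretion.

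Section 10.2 describes the per-protocol comparison in general terms: "only subjects that received the assigned intervention for 3 months will be included in comparisons". It then widens the set to children who came off medication in the first 3 months because of intolerance or toxicity.

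Two sections say what receiving the assigned intervention amounts to:

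- Section 8.2: "ondansetron and methotrexate in the intervention group, methotrexate in the control group".
- Section 9.3, intervention arm: "the patient received methotrexate and prophylactic ondansetron for at least 3 months". Control arm: "For the control group this means the patient received methotrexate for at least 3 months".

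Section 9.3 also says that a control may not be dropped for having taken ondansetron. That sentence belongs to the account of the intention-to-treat primary analysis.

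**The concern.** The treatment under test is prophylactic ondansetron. The per-protocol rule checks for it in the intervention arm and ignores it in the control arm. Treatment is open-label and ondansetron is available to controls, so a control can receive the intervention strategy in full and still be analysed as an adherent control. An intervention child who does not take prophylactic ondansetron drops out of the set unless early intolerance or toxicity keeps the child in.

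At stake is how the secondary per-protocol result can be read. It would normally be taken as the effect among children who followed their assigned strategy. With crossover screened in one arm only, it may sit closer to no difference than that effect. Because section 10.2 repeats every efficacy endpoint in this set, the rule touches the five secondary endpoints as well as the primary one.

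**Working it through.** **1. The rule against the assigned strategy**

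| Child, on methotrexate for at least 3 months | Followed the assigned strategy (6.1, 6.3)? | In the per-protocol set (8.2, 9.3)? |
|---|---|---|
| Intervention, with prophylactic ondansetron | Yes | Yes |
| Intervention, without it | No | No, unless the intolerance/toxicity exception applies |
| Control, no ondansetron or only after nausea/vomiting | Yes | Yes |
| Control, routine ondansetron from the start | No | Yes |

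The last row is the problem.

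**2. When crossover is unambiguous.** Section 6.2 excludes "Previous use of methotrexate", and section 10.1 notes that "the actual date the first methotrexate dose is given at home varies from family to family". At baseline no methotrexate-induced nausea can yet have occurred. Ondansetron started then for routine use before doses cannot be the as-needed strategy.

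**3. The plan's own figures.** No stated figure depends on this rule. Section 7 (50% v 75%, 90% power, 79 evaluable per arm) supplies the illustration. The log relative-risk formula with pooled null variance, p̄ = 0.625 and two-sided 0.05 (section 7 does not state sidedness) gives

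n = [1.960 × √(2 × 0.375/0.625) + 1.282 × √(0.25/0.75 + 0.50/0.50)]² / (ln 1.5)² ≈ 80,

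close to 79. Then 158/0.9 = 175.6, which rounds up to the stated 176.

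**4. Illustrative dilution.** Let c be the fraction of per-protocol controls who cross over and s their success probability; both are assumptions. Control success is 0.50(1 − c) + s·c, and intervention success is 0.75.

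| s | c = 10% | c = 20% |
|---|---|---|
| 0.75 | 0.525, RR 1.43 | 0.550, RR 1.36 |
| 0.625 | 0.5125, RR 1.46 | 0.525, RR 1.43 |
| 0.50 (no gain) | 0.500, RR 1.50 | 0.500, RR 1.50 |

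**5. Against sampling error.** SE(log RR) = √[0.25/(0.75n) + 0.50/(0.50n)]. At n = 79 this is 0.130. Section 15 reports 27 + 17 = 44 children at the interim; an assumed even split gives n = 22 and SE 0.246. With s = 0.75:

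- c = 10%: ln(1.50/1.429) = 0.049, or 0.38 SE at 79 per arm and 0.20 SE at 22. That is about 8 or 2 controls.
- c = 20%: ln(1.50/1.364) = 0.095, or 0.73 SE and 0.39 SE. That is about 16 or 4 controls.

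**6. What a remedy recovers.** Suppose a baseline rule catches half of the crossovers (s = 0.75). Control success is [0.50(1 − c) + 0.375c]/(1 − 0.5c): 0.513 (RR 1.46) at 10% and 0.528 (RR 1.42) at 20%.

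An exclusion that depends on nausea after randomisation can overshoot. If it removed only the crossovers who succeeded, control success would be 0.50(1 − c)/[(1 − c) + 0.25c]: 0.4865 (RR 1.54) and 0.4706 (RR 1.59), above the undiluted 1.50.

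**The case against.** The strongest reply is that the SAP never says the per-protocol analysis is meant to compare the strategies as followed. It describes a minimum-exposure set, and methotrexate is the one exposure every control must have, since ondansetron is permitted in control care. The rule is explicit and repeated consistently, so the analyst is not left guessing. No decision, power claim or success criterion rests on this analysis. No crossover is documented, and dilution toward 1 cannot create a false claim of benefit in a superiority trial.

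Most of this stands, and it is why the priority is low. It does not remove the inconsistency: section 10.2 restricts the set to children who received what they were assigned, and the control definition then leaves out the condition that distinguishes the control strategy. The general wording in 10.2 cannot rescue the rule either, because 9.3 says what it means for each arm and an analyst would code that.

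Two practical objections also stand. A prescription at baseline is not the same as prophylactic use; a family may hold it in reserve and use it only if nausea occurs. And with visits usually 1 to 4 months apart (section 5.2), ondansetron and nausea will often first appear at the same visit, so their order is unknown. Excluding on that order would also condition on nausea, which is closely tied to the intolerance endpoint.

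A reader might infer that every control who took ondansetron should leave the set. Sections 6.1 and 6.3 make ondansetron after nausea part of the assigned control strategy, so those children belong in it.

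**Conclusion.** The inconsistency is real and confined to the secondary per-protocol analysis. As written, the rule counts a control on routine ondansetron from the start as adherent and screens crossover in one arm only. If ondansetron works, the effect is to move the per-protocol relative risk toward 1. The amount is unknown: the figures above assume the section 7 success rates and invented crossover rates, and the shift is zero if crossovers gain nothing. In every case shown it is below one standard error, though always in the same direction.

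Three stronger conclusions are not supported. A reader might infer that the trial's main result is compromised; the primary analysis is intention-to-treat, and the interim rule and alpha do not use the per-protocol set. A reader might infer that crossover has happened; the SAP reports none. A reader might also translate the dilution into lost power (at 79 per arm, a Wald test at two-sided 0.05 goes from 88% with no crossover to 73% at 20%, with crossovers succeeding at 75%); the SAP claims no power for this analysis, and section 8.5.3 already doubts that the planned size can be reached.

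**What to change.** In sections 8.2, 9.3 and 10.2:

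1. State that a control prescribed or using ondansetron at baseline for routine use before methotrexate doses is not per-protocol, whatever the later outcome. Apply this before the intolerance/toxicity exception, so that membership does not depend on how the child fared.
2. State that a control with a just-in-case prescription, used only after nausea or vomiting, stays in. The physician and parent ondansetron reports (sections 9.5 and 10.2) separate the two.
3. Report the number of controls with ondansetron recorded before any recorded nausea or vomiting, classing a first appearance of both at the same visit as as-needed use. The physician adverse-event form in section 11 lists nausea/vomiting, and nausea treated with ondansetron fits its definition of an actionable event. Do not exclude children on this basis in the main per-protocol result.

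Leave the intervention-arm rule unchanged.

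The cost is a few sentences and one count. Section 6.4 already schedules ondansetron use and dose at baseline and every visit. The downsides are a slightly smaller per-protocol set and that crossover starting after baseline is not removed; the count in item 3 at least makes it visible.

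### The modified per-protocol rule selects early leavers on outcome, and its ondansetron condition deletes event-free children from the intervention arm alone

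*SAP*

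**What the plan says.** The per-protocol analysis is secondary. It repeats the primary endpoint and five secondary endpoints (SAP 10.2).

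- **Why it was changed.** At the interim analysis some children had stopped methotrexate early for intolerance, so "the per protocol analysis was modified to also include patients who stopped the medication before 3 months due to intolerance or toxicity" (SAP 8.2).
- **Entry.** SAP 9.3 admits those who "received the assigned intervention for at least 3 months or who experienced intolerance within the first three months". SAP 10.2 words it as "all patients receiving study medications for at least 3 months and all patients stopping medications before 3 months due to intolerance or toxicity"; section 10 agrees with 10.2.
- **Early leavers.** Patients who withdraw or are "lost to follow-up before 3 months are not included in the per-protocol analysis, unless they already experienced intolerance or toxicity" (SAP 9.3).
- **Exposure test.** "For the intervention group this means the patient received methotrexate and prophylactic ondansetron for at least 3 months". By contrast, "For the control group this means the patient received methotrexate for at least 3 months" (both SAP 9.3).
- **After 3 months.** "Patients who withdraw or are lost to follow-up after 3 months will be considered censored and have their data analyzed using Kaplan Meier survival methods" (SAP 9.3).
- **Failure.** Under SAP 8.5.3 and 10.1 a child fails with a MISS of 6 or more, by stopping methotrexate (temporary holds apart), or by stopping ondansetron or methotrexate for toxicity or lack of efficacy.

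**The concern.** Whether an early leaver belongs to the per-protocol set depends on the outcome that the set is used to estimate. Take two intervention children who both give up ondansetron at week 6, for a reason that is neither toxicity nor lack of efficacy, and stay on methotrexate. One scores 6 on the MISS at week 10: under 9.3 that child is in the set, as a failure. The other never becomes intolerant: that child is removed, together with all the event-free time. A control child has no ondansetron condition to miss, so nothing matches this deletion in the control arm.

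Loss to follow-up is treated in the same lopsided way before 3 months, but is censored afterwards. Removing event-free children from the early risk set while keeping the early events lowers a Kaplan-Meier success estimate, even if leaving has nothing to do with prognosis.

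At stake is the reading of the per-protocol result. A relative risk below the intention-to-treat figure could be taken as lack of benefit in children who followed their assignment, when the inclusion rule produced it.

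**Working it through.** **Inputs from the SAP.** Success is 75% with intervention and 50% with control (section 7), so the true relative risk (RR) is 0.75/0.50 = 1.50. The stated sample size is not in dispute: exact power at 79 per group is 0.903, and 158/0.9 = 175.6, rounded up to 176.

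**Assumptions, because the SAP gives no figures.**
- Half of all failures fall before week 13. Success at week 13 is then S13 = 1 − 0.5 × 0.25 = 0.875 (intervention) and 1 − 0.5 × 0.50 = 0.75 (control).
- A share s of intervention children, 0% to 30%, stop only ondansetron before week 13, for a reason that is not a failure and is unrelated to prognosis.
- 10% of each arm is lost before week 13. Section 7 allows up to 10% dropout without timing, so placing all of it early is the upper end.

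**Step 1: ondansetron-only stops, no loss.** Under 9.3 a stopper with early intolerance stays and a stopper without it goes, so s × S13 of the arm is deleted, all event-free:

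S13(per protocol) = S13 × (1 − s) / (1 − s × S13); S52(per protocol) = S13(per protocol) × S52/S13.

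For the intervention arm, S52/S13 = 0.75/0.875 = 0.857.
- s = 10%: 0.7875/0.9125 = 0.863; × 0.857 = 74.0%; RR 1.48
- s = 20%: 0.700/0.825 = 0.848; × 0.857 = 72.7%; RR 1.45
- s = 30%: 0.6125/0.7375 = 0.831; × 0.857 = 71.2%; RR 1.42

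With no true effect (50% in both arms, S13 = 0.75), the RR is S13(per protocol)/0.75: 0.730/0.75 = 0.97, 0.706/0.75 = 0.94 and 0.677/0.75 = 0.90.

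**Step 2: add 10% early loss in each arm** (simulation, loss and stops spread evenly over weeks 0 to 13). Control success becomes 49.3%. Intervention success is 72.1% at s = 20% and 70.5% at s = 30%.

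| Early ondansetron-only stops | RR, true value 1.50 | RR, true value 1.00 |
|---|---|---|
| 0% | 1.51 | 1.00 |
| 10% | 1.49 | 0.97 |
| 20% | 1.46 | 0.94 |
| 30% | 1.43 | 0.90 |

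With no such stops the RR is slightly too high, because equal loss lowers the control estimate more in relative terms. The two effects cancel at roughly 5% to 7%.

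**Step 3: sensitivity.**
- With 70% of failures early, the RR is 1.45 at 20% and 1.41 at 30%.
- Under the entry wording of 8.2, 10 and 10.2 (stopping because of intolerance), it is 1.48 and 1.47. The bias is smaller but has the same direction.
- If the stoppers are all children who would have succeeded, then without loss intervention success is (0.75 − s)/(1 − s), and the RR is 1.44, 1.38 and 1.29 at 10%, 20% and 30%.

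**Step 4: failures that the rule deletes.** Early methotrexate stops for lack of efficacy or other reasons fail the 3-month test and are not rescued by the exception. In the cohort cited in SAP 8.5.4, 59 children became intolerant and 11 stopped for other reasons, so 11/70 = 15.7% of failures were of this kind (an upper bound, as some may be toxicity). In the control arm, 0.25 × 0.157 = 3.9% of children would be deleted as early failures. Without loss, 0.75/0.961 × 0.50/0.75 = 52.0%; with 10% loss, 51.4%. Control success is then overstated.

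**The case against.** The strongest reply is that this is a supportive analysis, that the modification and its reason are disclosed, and that it improves on a rule that dropped early failures altogether. All of that is true. But the change restores early intolerance and toxicity without restoring the event-free children or the other early failures, so selection on outcome remains.

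The second reply concerns size. The SAP states no rate of ondansetron-only stopping, and at 10% or less the RR moves by about 0.01. That also stands, and it rules out three stronger readings that a reader might infer:
- That the rule understates success in both arms. Step 4 shows control success above 50%, because some early failures are deleted too.
- That the bias always works against ondansetron or always falls mainly on the intervention arm. With few ondansetron-only stops it runs slightly the other way.
- That the main result is compromised. Intention to treat is primary and does not use this rule.

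The third reply concerns the remedy. Censoring every stop for a reason other than intolerance or toxicity would turn methotrexate stops, which are endpoint failures, into censored observations. With the 15.7% share in both arms, success becomes 0.50^0.843 = 55.7% and 0.75^0.843 = 78.5%, and the RR 1.41. That is as large a distortion as the one being repaired, so the censoring must be narrower. Nor does 9.3 already censor at an ondansetron stop: after 3 months it censors only withdrawal and loss.

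**Conclusion.** The point holds as a defect of the secondary per-protocol analysis. Membership depends on outcome among children with under 3 months of the assigned intervention, and the unequal exposure test removes event-free children from one arm only. Both features are explicit in the SAP; choosing between its two entry wordings changes the size and leaves the defect in place.

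The size is uncertain. Under the stated assumptions the RR runs from 1.51 to 1.43 against a true 1.50 as early ondansetron-only stops rise from 0% to 30%, and falls to about 0.90 at 30% when there is no true effect. It rests on assumed stopping rates, on half of failures being early, on all 10% loss being early, and on stopping being unrelated to prognosis. The change is worth making because it is cheap.

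**What to change.** In SAP 8.2, 9.3, 10 and 10.2, replace the 3-month inclusion rule with the following.

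- **Set:** all randomized children who started their assigned intervention.
- **Failure:** the primary-endpoint definition, unchanged, at any time up to week 52: a MISS of 6 or more, any non-temporary methotrexate stop, or stopping ondansetron for toxicity or lack of efficacy.
- **Censoring:** only at the last visit before withdrawal or loss or, in the intervention arm, at the visit where ondansetron is first recorded as stopped for a reason that is not itself a failure while methotrexate continues.
- **Secondary endpoints:** censored at the same dates.

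Under the assumptions above this returns an RR of 1.50, including when 15.7% of failures are methotrexate stops for other reasons. It also removes the difference between the entry wordings. The statement in 10.2 that the two analyses differ only in who is included needs a matching edit.

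The cost is SAP wording and one derived date. Methotrexate and ondansetron use are recorded at every visit (SAP 6.4), and the reason for an ondansetron stop is already needed for the primary endpoint (10.1). The downside is that censoring at an ondansetron stop is new to this SAP, may be informative (for example if children stop because they feel well), and is dated only to the visit, with visits usually 1 to 4 months apart. Report the result beside the intention-to-treat result with that caveat.
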